10.2 Lost to Follow Up

Sites will contact patients for each visit in accordance with the procedure outlined in section 13.2. If patients are not able to be contacted after three missed regular (fortnightly or monthly) GOSE assessment, a letter will be sent out to the participant asking them to get in contact with the trial team. Participants will not be contacted again until the 3 month, 12 month, or annual follow up occurs. Sites will record all details regarding attempts to contact the participant on the appropriate CRF. To minimise missing data, participants will be able to complete the primary outcome online or over the phone. In addition, contact details for participant's study partner will be collected and they will be able to complete the primary outcome on behalf of the participant. All data from participants will be collected regardless of their adherence to the protocol.

11 Trial Intervention

Patients will receive IVIG (2g/kg over 5 days) or placebo (Saline solution).

IVIG is a preparation of antibodies made from blood donations. It is licensed for use in patients with primary and secondary immunodeficiencies and for certain neurological conditions, such as Guillain-Barré syndrome. IVIG is given to many patients with autoimmune encephalitis. However, its efficacy is not known, and being a blood product, it carries risk of side effects.

We choose 2g/kg IVIG over 5 days (0.4g/kg/day for 5 days) because it is the dosing regimen most commonly used in neuro-inflammatory conditions, including in Guillain-Barré syndrome, and is the dose used in the pilot study of IVIG in encephalitis (Rayamajhi et al., 2015).

All patients will also receive methylprednisolone 1g daily intravenously for 5 days, followed by 1mg/kg (up to 60mg daily maximum) oral prednisolone daily for two weeks, followed by a taper regime (see section 11.4 for full dosing schedule).

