Primary objective	To determine if early treatment with IVIG changes the time to recovery as measured on the Glasgow Outcome Scale - Extended (GOSE).		

Secondary objectives	To determine the effect of IVIG on the clinical condition, GOSE, health utility, and self-rated health of all patients at 3 and 12 months, and to follow up a subset of patients annually. To determine the effect of IVIG on the modified Rankin Scale, Liverpool outcome score,			
	and neuropsychological outcomes at 12 months.			
	To determine the effect of IVIG on the rate of adverse events, time to hospital discharge, use of further immunotherapy, rate of relapse, and rate of mortality.			
Tertiary/Exploratory objectives	Exploration of the mechanistic action of IVIG			
	To better understand the development of later consequences such as epilepsy and psychiatric illness (to be funded and reported separately)			
Primary outcomes	Time from randomisation to achievement of a GOSE score of 5 or more, maintained for two sequential assessments (assessed fortnightly for 3 months, and then monthly for up to 12 months or until GOSE 5 reached for two consecutive assessments. Maximum number of assessments: 15)			
Secondary outcomes	 GOSE at 3 and 12 months post-randomisation Clinical outcomes: a. Adverse events, b. Time to hospital Discharge, c. Use of further immunotherapy (IVIG, steroids, plasma exchange, other), d. Clinically defined relapse, e. HDU/ITU admission, f. Seizures g. Use of ventilator support h. Mortality Neuropsychological outcomes Health utility and self-rated health 			
Tertiary/Exploratory outcomes	Exploration of the mechanistic action of IVIG			
Investigational medicinal products	IVIG (2g/kg over 5 days) or placebo (0.9% Saline).			
Non-Investigational Medicinal Products	All patients will also receive methylprednisolone 1g daily intravenously for 5 days, followed by 1mg/kg (up to 60mg daily maximum) oral prednisolone daily for two weeks, and then followed by a taper regime (reduction in 10mg decrements per week until 10mg, then reducing in 1mg every week until stop).			
Form	Intravenous Infusion			
Dose	2 g/ kg over 5 days			
Route	IV			

[figure not shown]

3 Trial summary & schema

3.1 Trial schema: Enceph-IG- Intravenous Immunoglobulin in Autoimmune Encephalitis in Adults A Randomised Double-Blind Placebo-Controlled Trial

Primary outcome:

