5.3 Primary outcomes measure(s)

The primary outcome is time to recovery defined as achieving a score of 5 or greater on the GOSE for two assessments in a row. The current trial will use a web-based version of the GOSE, which was pilot tested with 229 encephalitis patients and families. The scale will be administered every two weeks for 3 months and then monthly up to 12 months post randomisation or until they reach the primary endpoint. All participants will complete the GOSE at 3 months and a subset of participants will complete it 12, 24, 36, and 48 months post randomisation even if they have achieved the primary end point.

The GOSE is a measure of functional outcome and is validated for the assessment of brain injured patients via telephone or postal questionnaire. GOSE ranges from 1 (death) to 8 (full recovery), with 5

meaning able to live independently. The Glasgow Outcome Scale and GOSE have been used in many brain injuries, including autoimmune encephalitis (Ramanuj et al., 2014). GOSE is used in the Enceph-UK and DexEnceph studies. It has been validated for assessment in brain injured patients previously using telephone and postal questionnaires. In this study we have converted this to a web-based format.

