12.1 Cytogenetics and Molecular Genetics

DNA will be extracted from participant's blood samples. See Figure 2 for amounts and vials required. DNA (EDTA sample) will be stored on patients for future genetic disease association studies. These future studies will look whether genetic polymorphism within patients, particularly within a region of the DNA called the Human Leukocyte Antigen (HLA) system, are linked to different clinical outcomes.

13 Trial procedures

Follow up assessments will place take place at weeks 2, 4, 6, 8, and 10, and then at months 3, 4, 5, 6, 7, 8, 9, 10, 11, and 12, 24, 36, and 48 post randomisation. All patients will complete the 2 weeks and 3 months follow up. The number of fortnightly assessments completed will depend on when they reach the primary endpoint and the number of monthly follow ups completed when they are recruited (see section 13.2 for time point cut-offs for assessments). Data collection be completed 3 months after the last patient is recruited.

Along with the main trial, there will be a mechanistic study looking at the role of glycosylation of the IgG Fc region. Samples will be taken at baseline and 2 weeks and then compared to samples from healthy volunteers who have undergone a lumbar puncture for non-inflammatory conditions. The CSF samples from healthy volunteers will be requested from the Walton Research CSF biobank. The biobank is managed by the Walton Centre NHS Foundation Trust, has full ethical approval from Wales REC4 and all samples are kept under the Human Tissue Authority License. The biobank request will be made independent of this trial and protocol. Full details of the mechanistic study can be found in section 19.

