13.2 Follow-up

Data collection will continue for all patients until 3 months after the last patient is recruited. The primary outcome measure will be collected fortnightly for the first 3 months for all participants, and then monthly until 12 months post-randomisation for a subset of participants, unless participant reaches primary endpoint. A subset of participants will also complete the GOSE annually until the end of the trial. Clinical follow up assessments and assessments of self-rated health will be completed at 3 month for all participants, and then at 12 months and annually for a subset of participants. Participants recruited after month 45 of recruitment, will complete all assessments up to and including the 3 month assessment. Patients recruited up until month 44 of recruitment will complete all assessments up to and including the 12 month assessment, patients recruited up until month 32 of recruitment will complete all assessments up to and including the 36 month assessment. Those patients recruited up to month 8 of recruitment will complete all assessments up to and including the 48 month assessment. A detailed schedule of the assessments can be found in figure 3 in section 13.1.

For the fortnightly assessments, the follow up window is ±2 days. Participants will be notified 1 day before the follow up window starts and then again on the first day of the follow up window. If the participant does not complete the assessment on the first day, they will be contacted every day until they complete the assessment or the follow up window closes. For the monthly assessment, the follow up window is ±7 days. The same procedure will be used, except if participant doesn't complete the assessment on day 1 of the follow up window, they will be contacted every other day until the window closes. Any assessments that require in person attendance must be scheduled within the appropriate follow up window. Participants will be contacted at each assessment time point regardless of whether they completed the previous assessment point unless they withdraw their consent to take part in that section of the trial or the trial as a whole.

14 Internal pilot and recruitment rates

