16.4 Missing, unused & spurious data

Our primary outcome will be analysed as a time-to-event variable, with missing observations censored at the final time at which data were available.

Further detail is provided in the ENCEPH-IG Statistical Analysis Plan (SAP).

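### Section 10.2 suspends regular GOSE contact after three missed assessments while section 13.2 keeps it at every time point; under 10.2 some recoveries cannot be confirmed

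*Protocol*

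**What the plan says.** Section 10.2 (Lost to Follow Up) begins: "Sites will contact patients for each visit in accordance with the procedure outlined in section 13.2". It then sets a special rule: "If patients are not able to be contacted after three missed regular (fortnightly or monthly) GOSE assessment, a letter will be sent out", and after the letter, "Participants will not be contacted again until the 3 month, 12 month, or annual follow up occurs". The same section allows the primary outcome to be completed online, by phone or by the study partner.

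Section 13.2 (Follow-up) says: "Participants will be contacted at each assessment time point regardless of whether they completed the previous assessment point". The one exception it names is withdrawal of consent from that part of the trial or from the whole trial.

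Section 5.3 defines recovery as "achieving a score of 5 or greater on the GOSE for two assessments in a row", and section 17.1 ties the two consecutive scores to the assessment schedule. Section 16.4 analyses the outcome as time to event, "with missing observations censored at the final time at which data were available".

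**The concern.** The two sections give incompatible contact rules for the primary outcome, and section 10.2 conflicts with its own first sentence. Neither section says which prevails. An analysis plan cannot settle it, because the conflict is about which data are sought.

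It matters because one good score is not an event. A participant contacted only at the fixed visits may give a GOSE of 5 or more at month 12 and still not be counted as recovered, because no adjacent score was sought. That participant is censored at the last available data.

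Such censoring is plausibly informative. Section 9.3 describes impaired memory in this disease, and people may stop responding because they are unwell or because they are back to normal life. Section 10.1 lists leaving the regular GOSEs while keeping the 3-month, 12-month and annual visits as something a participant may choose. Section 10.2 imposes the same pattern on people who did not ask for it.

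**Working it through.** **Step 1: the schedule.** Section 13 (Trial procedures) places assessments at "weeks 2, 4, 6, 8, and 10, and then at months 3, 4, 5, 6, 7, 8, 9, 10, 11, and 12" (later annual visits follow). That is 5 + 10 = 15, which agrees with the Synopsis: "Maximum number of assessments: 15".

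**Step 2: trial-initiated contacts left up to month 12, by time of the third miss.** Adjacent pairs are in brackets. Section 10.2 is read two ways, because it does not say whether regular contact resumes after the 3-month visit.

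| Third miss | 13.2 | 10.2, no resumption | 10.2, resumes at month 3 |
|---|---|---|---|
| Week 6 | 12 (11) | months 3 and 12 (0) | 10 (9) |
| Week 8 | 11 (10) | months 3 and 12 (0) | 10 (9) |
| Week 10 | 10 (9) | months 3 and 12 (0) | 10 (9) |
| Month 3 | 9 (8) | month 12 (0) | 1 (0) |
| Month 6 | 6 (5) | month 12 (0) | 1 (0) |
| Month 10 | 2 (1) | month 12 (0) | 1 (0) |
| Month 11 | 1 (0) | month 12 (0) | 1 (0) |

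- From month 3 to month 10, section 13.2 leaves at least one pair and section 10.2 leaves none on either reading.
- At weeks 6 to 10 the result depends on resumption. With it, the fortnightly contacts before month 3 are lost after a third miss at week 6 or 8, and nothing is lost at week 10. Without it, no pair is left.
- At month 11 the two rules leave the same single contact.

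Participants recruited after month 45 of recruitment are followed only to 3 months (section 13.2). After a third miss at week 6, 8 or 10, section 13.2 leaves 3, 2 or 1 contacts and section 10.2 leaves 1 each time. No pair is possible under 10.2. Compared with 13.2, the loss arises at weeks 6 and 8.

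**Step 3: reproduce the sample size.** Inputs from section 16.3: two-sided alpha 0.05, power 85%, hazard ratio 1.43, 20% not recovered by 12 months (read as the placebo arm), 5% drop-out.

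- Events (Freedman): (1.960 + 1.036)² × (2.43 / 0.43)² = 287.
- Event probability: placebo 0.80; IVIG 1 − 0.2^1.43 = 0.90; mean 0.85.
- 287 / 0.85 = 338 participants; 338 / 0.95 = 356, the planned number.

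**Step 4: sensitivity of power to loss.** The protocol gives no rate for the three-miss rule. ASSUMPTION: total loss from all causes is 5% to 25%, and lost participants contribute no event (worst case). Events = 356 × (1 − loss) × 0.85, using the unrounded 0.8499. Power = Φ(√events × 0.43 / 2.43 − 1.96).

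| Total loss | Events | Power | N for 85% power |
|---|---|---|---|
| 5% | 287.5 | 85.1% | 356 |
| 10% | 272.3 | 83.2% | 376 |
| 15% | 257.2 | 81.0% | 398 |
| 20% | 242.1 | 78.6% | 423 |
| 25% | 226.9 | 76.0% | 451 |

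**The case against.** The trigger is narrower than three missed forms: the participant must also be out of reach. Each miss will already have followed reminders to participant and study partner and repeated calls (sections 13.1 and 13.2), and inpatients are assessed at the bedside. Section 10.2 can therefore be read as an unstated exception for people who are hard to reach, and limiting contact with them is a defensible choice about burden. The letter, online completion and the study partner remain as ways back. The data monitoring committee reviews GOSE completion at each meeting (section 24.4), the pilot has a retention criterion (section 14.1), and section 17.1 plans analyses for data missing at random and not at random.

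Much of this stands, and it limits the size of the effect. It does not remove the conflict. Section 13.2 states its exception and this is not it. Monitoring reveals gaps without closing them, and sensitivity analyses cannot recover scores that were never sought.

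A reader might infer that the endpoint becomes unobservable for everyone who misses three assessments. The documents do not support that: regular contact may resume after month 3, other routes of completion stay open, and a third miss at month 11 costs nothing compared with section 13.2. A reader might also infer that the rule by itself takes power to 81%. That figure needs 15% total loss, partly overlapping the 5% already allowed, with all of the excess charged to this rule as though section 13.2 would have recovered every lost event.

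**Conclusion.** The contradiction is certain from the text, and the passages must be reconciled. Under section 10.2, trial-initiated contact cannot confirm recovery after a third miss from month 3 to month 10, or after any third miss in participants followed only to 3 months. For earlier third misses, confirmation is delayed at weeks 6 and 8 if regular contact resumes at month 3, and missed at weeks 6 to 10 if it does not. This takes two assessments in a row to mean adjacent scheduled ones, as section 17.1 indicates.

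The number affected is unknown. The power range of about 85% to 76% describes total loss of 5% to 25% under a worst-case assumption. Only the difference between the two contact rules belongs to this point, and for people who did not respond to three rounds that difference may be small. Informative censoring is plausible but cannot be sized from the documents. The planned sample size of 356 is not in question. The change is worth making because it protects ascertainment of the primary outcome at little cost.

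**What to change.** Delete from section 10.2 the sentence that bars further contact until the next fixed visit. Keep the letter after three misses. State that section 13.2 continues to apply: the online link and contact attempts to the participant or study partner go on at each scheduled GOSE until the endpoint is reached, follow-up ends or consent is withdrawn.

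This is a one-sentence amendment, and the automated alerts and phone follow-up already exist. The downside is some additional reminders and calls to people who have not responded; those who do not want them can withdraw from the regular GOSEs under section 10.1.

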11.1 Treatment(s)

The trial is being carried out under a CTA. The drug is therefore only to be used by the named investigators, for the participants specified in this protocol, and within the trial. Sites may use any brands in accordance with local hospital policy. IVIG comes as a sterile clear, or slightly opalescent and colourless to pale yellow solution, which is isotonic, with an approximate osmolality of 320 mOsmol/kg. IVIG is licensed for use in the UK. Despite being commonly used to treat autoimmune encephalitis, it is not currently licensed for this use. IVIG comes in ready to use single use vials, containing 10g/100ml

solution which does not need to be diluted and contains human protein of which at least 98% IgG, trace amounts IgA (no more than 25 micrograms/ml), and is essentially sodium free. Other ingredients are amino acid proline and water. The responsibility for the safety profile, including screening for COVID-19, of the IVIg will lie solely with the manufacturers of the product.

The placebo is saline solution. The solution will contain 0.9% sodium chloride. The placebo will be bottled in matched 100ml single use vials. Placebo bottles should be stored below 30°C in all original packaging.

The current trial will use a Summary of Product Characteristics. Sites should ensure to consult the appropriate SmPC for clinical management decisions.

Patients will receive an infusion via IV of IVIG (2g/kg over 5 days) or placebo (saline solution). All patients will also receive methylprednisolone 1g daily intravenously for 5 days, followed by 1mg/kg of body weight, with a maximum dose of 60mg, oral prednisolone daily for two weeks. This will be followed by a taper regime (see section 11.4 for full dosing schedule).

For the first 14 days post randomisation, all other immunomodulatory treatment should be avoided. Once the 14-day period has elapsed, anti-neuronal antibody results will be reviewed and assessment on whether the patient has improved, stabilised or deteriorated will be made. If deemed necessary further non-IVIG treatment such as steroids, or plasma exchange will be considered. IVIG may be an option only after these alternatives have been considered. This procedure will be used in the event of subsequent deterioration or in the event the treating clinician determines additional treatment is necessary.

Figure 1 Treatment Schedule

Treatment	IVIG or	Methylprednisolone	oral	Recovery	Further Treatment
Day	Placebo		prednisolone	Assessment	
1	0.4g/kg	1g			
2	0.4g/kg	1g			
3	0.4g/kg	1g			
4	0.4g/kg	1g			
5	0.4g/kg	1g			
6			1mg/kg (max		
			60mg)		
7			1mg/kg (max		
			60mg)		
8			1mg/kg (max		
			60mg)		
9			1mg/kg (max		
			60mg)		
10			1mg/kg (max		
			60mg)		

11	1mg/kg (max 60mg)	
12	1mg/kg (max 60mg)	
13	1mg/kg (max 60mg)	
14	1mg/kg (max 60mg)	
15	1mg/kg (max 60mg)	If participant hasn't improved
16	1mg/kg (max 60mg)	If participant hasn't improved
17	1mg/kg (max 60mg)	If participant hasn't improved
18	1mg/kg (max 60mg)	If participant hasn't improved
19	1mg/kg (max 60mg)	If participant hasn't improved
20	1mg/kg (max 60mg)	If participant hasn't improved
21	Start Taper Regime	If participant hasn't improved

If, for reasons relating to patient safety, a clinicians deems it is necessary to provide additional rescue treatment within the 14 day window post randomisation or to administer IVIG at any point they must alert the central trial team by emailing [contact] within a week and record the information on the appropriate CRF. This, by itself, will not constitute a reason to withdraw the patient from the trial.

11.2 Treatment supply and storage

IVIG and Placebo:

Sites will use their standard hospital stock of IVIG. To maintain the blind both IMP and placebo will be packaged and labelled identically and in sequentially numbered packages. The labelling will be in accordance with Annex 13 of the Rules Governing Medicinal Products in the EU: Manufacturing Practices. The sequential numbering will remain on the packaging to allow for emergency unblinding. The manufacturing pharmacy unit will also be responsible for the final QP certifications for placebo. The manufacturing pharmacy unit will be responsible supplying the individual sites with the placebo.

Storage for IVIG will be in accordance with its SmPC. Once opened, IVIG should be infused immediately as it contains no preservatives. It is able to be stored in its original packaging for up to 3 years. Sites should follow standard local practices for monitoring temperature.

Steroids:

Steroids will be provided as part of standard care. Therefore, standard hospital stock will be used and stored according to local practices and relevant summary product characteristics. Annex 13 labelling and accountability is not required.

11.3 Treatment prescribing and dispensing

IVIG

Sites will use their hospital stock of IVIG. The placebo will be distributed to each site pharmacy by the manufacturing pharmacy unit. A drug receipt log must be maintained and will log at minimum date of delivery and person accepting shipment. The logs will be returned to the CTR for monitoring. An IMP inventory log will also be provided. Sites can use their own logs as well as all necessary information is captured.

Once a patient is randomised, a randomisation email will be sent to the unblinded pharmacist who will prepare the correct vial for dispensing. They will ensure the tear off section of the label, that labels bottle as IMP or placebo, is removed and that the packaging is adequately sealed to maintain the blind. The bottles will be labelled with a number that will allow for emergency unblinding. The trial prescription should contain at minimum the following information:

- Participant study ID
- Participant Initials
- Date
- Dose Number
- Participant DOB
- Participant's weight
- Total Calculated amount of IMP to be infused (in grams)

Steroids:

Steroids will be dispensed using standard local hospital procedure and prescriptions.

